6.1.5 Pharmacokinetic Analyses

Non-linear mixed-effects modeling will be used to analyze the dose concentration–time data of gantenerumab. Information from other studies in humans may be incorporated to establish the PK model. The selection of parameters and the derivation of individual measures of exposure, such as $AUC_{0-\tau}$, C_{max} , and C_{trough} , will depend on the final PK model used for this analysis. All PK parameters will be presented by listings and descriptive summary statistics, including the arithmetic mean (for $AUC_{0-\tau}$, C_{max} , and C_{trough}), median, range, SD, and CV. Details of the mixed-effects modeling analysis will be described in the Modeling and Simulation Analysis Plan and results of this analysis will be reported separately. The influence of background medication on the pharmacokinetics of gantenerumab will be explored and, if appropriate, concentration–effect relationships may be assessed post hoc for PD, efficacy, or safety measures.

6.1.6 Exploratory Analyses

An analysis will be performed to explore association of the treatment effect with patient genotypes to assess the influence of the APOE $\epsilon 4$ status and $Fc\gamma$ receptor genotypes on the gantenerumab treatment effect, the primary efficacy variable, and selected safety parameters and summarized by each of the genotypes. Inferential statistics may be applied in case the difference is clinically relevant.

6.1.7 Subgroup Analyses

Since this is a global study, the effect of some demographic variables and baseline characteristic such as race and region on efficacy and safety will be summarized within subgroups using descriptive statistics (please see subgroups below). Additional exploratory analyses of efficacy results may be performed using an MMRM model, with the subgroup, a treatment-by-subgroup interaction term, and a subgroup-by-time interaction terms included along the independent effects described above. This

exploratory subgroup analysis may be important in understanding the effect of these variables on efficacy and safety. Such exploratory analyses will be performed primarily in the case where the descriptive statistics results indicate substantial differences between the subgroups.

The following variables will be used to define the subgroups for these analyses:

- Sex
- Age
- Race
- APOE ϵ 4 status
- Fc γ receptor genotype
- Region

Additional subgroup analyses may be performed with subgroups defined based on baseline levels of CSF t-tau, p-tau, t-tau to A β 1–42 ratio, and p-tau to A β 1–42 ratio.

Since Part 1 (i.e., the double-blind period) has been suspended and replaced by an OLE, the primary and key secondary efficacy analyses will not be performed. However, exploratory and descriptive analyses will be conducted at the end of Part 1.

6.2 ANALYSES IN PART 2

As Part 2 is an OLE, regular safety analyses will be conducted as described in Section 6.1.4. In addition, descriptive statistics and changes from baseline will be used to explore clinical findings (including efficacy, global functioning, and biomarkers). PK analysis will be conducted according to Section 6.1.5.

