1. BACKGROUND

This document describes the statistical data that will be reported in the Clinical Study Report (CSR) for double blind treatment (Part 1) of Study WN28745 and will focus on the statistical methodology underlying the report. The efficacy and safety endpoints that will be the basis for comparing treatments will be defined in full in this document along with the populations of patients that are to be used in the analyses.

Dosing in study WN25203, investigating gantenerumab in prodromal Alzheimer's Disease (AD), was stopped in December 2014 due to a futility analysis. Consequently, recruitment into study WN28745 was stopped early. The final patient was randomized into study WN28745 on the 9th December 2015. Patients active in study WN28745 continued to receive study treatment until they discontinued from the study, finished the study, or transferred into the open label extension (OLE).

Although there will be reporting of study data in a variety of contexts beyond that of the CSR, such as the independent Data Monitoring Committee (iDMC), this document will not cover those contexts.

The description of layouts for the CSR outputs, the details about the underlying analysis datasets and programs, and the linking of production outputs to sections in the CSR are not within the scope of this document and will be covered in separate documents.

The language used in this statistical analysis plan (SAP) supersedes that in the protocol and protocol synopsis.

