4.4.1 Primary Efficacy Endpoint

The co-primary efficacy outcome measures are:

- The difference between Gantenerumab and Placebo treated patients in the mean change in ADAS-Cog 13 from baseline (Day 1) to Week 104 in the population of all randomized patients.

- The difference between Gantenerumab and Placebo treated patients in the mean change in ADCS-ADL from baseline (Day 1) to Week 104 in the population of all randomized patients.

For each of the co-primary endpoints, the absolute values, change from baseline and percentage change from baseline will be summarized by time-windowed visit.

In addition, the co-primary endpoints will also be analysed using a mixed model with repeated measures (MMRM). The model will use an unstructured variance – covariance matrix for the repeated measures allowing the inclusion of individuals with incomplete data. The following variables will be included in the modelling:

Dependant variable	ADAS-Cog 13 or ADCS-ADL
Independent variables	Treatment (placebo or Gantenerumab) APOE status (carrier or non-carrier) Baseline ADAS-Cog 13 or ADCS-ADL score Time (weeks relative to first dose in study) Treatment (placebo or Gantenerumab) by time (weeks relative to first dose in study) interaction

Patient, treatment and time will be treated as class variables. All data from all patients (as defined in Section 2.2) will be used, including data from Week 104/early termination visits.

A treatment-by-time interaction contrast will be used to estimate the difference between gantenerumab and placebo in the mean change from baseline at each visit. Least square means, standard errors, 95% confidence intervals will be reported for gantenerumab relative to placebo.

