4.5.8 Sub-group analysis

All safety and efficacy analysis will also be performed in the sub-group of patients who were enrolled in Japan and by APOE e4 carrier/non-carrier status.

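### Observed descriptive differences decide which exploratory subgroup interactions are modelled, and Part 1 SAP 4.5.8 neither withdraws that rule nor mentions most of the listed variables

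*Protocol*

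**What the plan says.** **Protocol 6.1.7** (repeated in the synopsis) starts with descriptive summaries within subgroups. "The following variables will be used to define the subgroups for these analyses": sex, age, race, APOE ε4 status, Fcγ receptor genotype and region. A modelling step may follow: "Additional exploratory analyses of efficacy results may be performed using an MMRM model", with subgroup, treatment-by-subgroup and subgroup-by-time terms. The condition for that step is: "Such exploratory analyses will be performed primarily in the case where the descriptive statistics results indicate substantial differences between the subgroups". What counts as substantial is not defined. Four CSF measures are optional: "Additional subgroup analyses may be performed with subgroups defined based on baseline levels of CSF t-tau, p-tau", and the ratio of each to Aβ1–42.

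**Protocol 6.1.6** (also repeated in the synopsis) plans an analysis of whether APOE ε4 status and Fcγ genotype modify the treatment effect, and then adds: "Inferential statistics may be applied in case the difference is clinically relevant".

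Section 6.1.7 closes by withdrawing the primary and key secondary efficacy analyses and keeping exploratory and descriptive ones.

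**Part 1 SAP.** Section 1 says: "The language used in this statistical analysis plan (SAP) supersedes that in the protocol and protocol synopsis". Section 4.5.8 says: "All safety and efficacy analysis will also be performed in the sub-group of patients who were enrolled in Japan", and adds analyses by APOE ε4 carrier status. These do not depend on results. For the mixed model for repeated measures (MMRM), section 4.4.1 says: "Least square means, standard errors, 95% confidence intervals will be reported for gantenerumab relative to placebo". The SAP names no treatment-by-subgroup interaction and no subgroup p-value.

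**The concern.** Under the protocol's rule, an interaction is modelled mainly when the same patients' data already show a large difference. An estimate that is reported because it was large does not keep its nominal error rate or interval coverage, and on average it is too far from zero. The interactions with small descriptive differences would mostly have no model-based estimate beside them, so a reader could not put the selected ones in context.

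Part 1 enrolled 389 of about 1000 planned patients, so chance differences between subgroups are large relative to the planned treatment effect. What is at stake is how exploratory subgroup findings are read. No confirmatory claim depends on them.

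**Working it through.** **1. The plan's own figure.** The documents state no error rate for subgroup tests. The only design figure is at least 80% power for each co-primary endpoint (Protocol 6.1.1). With 500 × 0.7 = 350 evaluable per arm, power is 83.3% for ADAS-Cog13 (2.3 points, SD 10.4) and 85.9% for ADCS-ADL (2.5 points, SD 10.9). The figure reproduces but does not bear on this point.

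**2. Which rule covers which variable.**

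| Variable | Protocol 6.1.6 and 6.1.7 | Part 1 SAP 4.5.8 |
|---|---|---|
| APOE ε4 status | Descriptive; model or inference depends on results | Analysed by status regardless of results; no interaction named |
| Fcγ genotype | Descriptive; model or inference depends on results | Not mentioned |
| Sex, age, race, region | Descriptive; model depends on results | Not mentioned |
| Four CSF measures | Optional | Not mentioned |
| Japan | Not listed | Analysed regardless of results |

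The only treatment-by-subgroup model in either document is the results-dependent one.

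**3. Rejection rate among the tests run, with no true interaction.** Assume a two-sided 0.05 test. Let c be the trigger in SEs and ρ the correlation between the descriptive difference and the interaction estimate. The documents give neither c nor ρ. For ρ = 1 and c ≤ 1.96 the rate is 0.05 / P(|Z| > c):
- c = 0.5: 0.05 / 0.617 = 8.1%
- c = 1: 0.05 / 0.317 = 15.8%

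Simulation (4 million draws) gives:

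| ρ | c = 0.5 | c = 1 | c = 1.5 |
|---|---|---|---|
| 1 | 8.1% | 15.8% | 37.5% |
| 0.9 | 8.1% | 15.6% | 33.0% |
| 0.7 | 7.6% | 12.7% | 21.4% |
| 0.5 | 6.5% | 9.2% | 13.3% |
| 0 | 5.0% | 5.0% | 5.0% |

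**4. Is a trigger near 1 SE plausible?** Protocol 6.1.1 calls its planned treatment differences clinically relevant. Suppose a 2.3-point ADAS-Cog13 difference between subgroups were the trigger. With two equal subgroups, equal arms and the planning SD, the SE of the interaction is 4 × SD / √N.
- N = 389: 4 × 10.4 / √389 = 2.11 points. The trigger is 2.3 / 2.11 = 1.09 SE, and the rate is 0.05 / 0.276 = 18%.
- N = 389 × 0.7 = 272: the SE is 2.52 points. The trigger is 2.3 / 2.52 = 0.91 SE, and the rate is 0.05 / 0.363 = 14%.

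Uneven subgroups or fewer evaluable patients raise the SE, which lowers the trigger in SE units and brings the rate closer to 5%.

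**5. Overstatement of true interactions.** For c = 1 to 1.5 and ρ = 0.7 to 1, the mean reported estimate divided by the true value is:
- 1.46 to 2.06 for a true interaction of 1 SE
- 1.10 to 1.25 for 2 SE
- 1.02 to 1.07 for 2.8 SE

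**6. What the rule does not change.** The chance that a variable is both modelled and significant is P(modelled) × the rate in step 3. At c = 1 this is 0.317 × 0.158 = 5.0% for ρ = 1 and 0.317 × 0.127 = 4.0% for ρ = 0.7. It never exceeds 5%. If every test is run and the tests are independent, the chance of at least one false positive is 1 − 0.95⁶ = 26.5% for six variables and 1 − 0.95¹⁰ = 40.1% for ten. The rule leaves these figures the same or lowers them: for six variables, c = 1 and ρ = 0.7, the chance is 21.7%.

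**The case against.** The strongest objection is that the Part 1 SAP says it supersedes the protocol, contains no results-dependent trigger, fixes two subgroup analyses in advance, and reports intervals without naming p-values. One natural reading is that the other variables were dropped. Part of this stands. A reader might infer that the planned Part 1 report will contain subgroup tests with a false-positive rate well above 5%. The documents do not support that, because the SAP plans no such tests. But SAP 4.5.8 does not say that the protocol rule or the other variables are withdrawn, and Protocol 6.1.7 still says those variables will be used. Leaving out p-values does not settle the matter either, because a confidence interval computed after selection also loses its nominal coverage.

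Three further inferences are tempting and not supported:
- **That the rule produces extra significant findings.** Step 6 shows that it does not. Where the descriptive difference is the tested contrast and the trigger is below 1.96 SE, every result significant under the rule would also be significant without it.
- **That subgroups which look alike go unreported and the number screened is hidden.** Section 6.1.7 promises descriptive summaries for all six listed variables. Only the model-based interaction is conditional, and only the CSF measures are optional.
- **That the inflation is certain.** In 6.1.7 the differences between subgroups could be read as differences in outcome level. If those are unrelated to the interaction, the rate stays at 5%. Section 6.1.6 leaves less room for this reading, because its subject is the treatment effect by genotype.

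It is also fair that the protocol makes this modelling optional, labels it exploratory and says only that it is done primarily in such cases.

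**Conclusion.** The point holds in limited form. The protocol lets the observed data choose which exploratory interactions are modelled, and the Part 1 SAP leaves unclear whether that rule survives for sex, age, race, region and Fcγ genotype. If the descriptive difference is the contrast then tested, about 8% to 16% of the tests run would reject under the null at an assumed trigger of 0.5 to 1 SE. A stricter trigger gives more, and a weaker correlation brings the rate down towards 5%. Interactions of about 1 SE would be overstated by roughly half to double; those of 2 SE or more by 25% at most.

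These sizes rest on an assumed trigger, an assumed correlation and an assumed two-sided 0.05 level, none of which the documents give. The inflation is conditional on a test being run: the rate per variable stays at or below 5%. Familywise error comes from the number of variables, not from this rule.

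**What to change.** - Delete the results-dependent sentences in Protocol 6.1.7 and 6.1.6 and their synopsis copies.
- Reconcile these sections with SAP 4.5.8, so that one list of subgroup variables applies to Part 1.
- Fit the treatment-by-subgroup interaction for every listed variable on both co-primary scales, whatever the descriptive results show. Six variables and two scales give 6 × 2 = 12 interactions per time point, with more estimates where a variable has more than two levels.
- Report all estimates with 95% CIs in one table, labelled exploratory, with the number of comparisons stated. If CSF measures are used, name them in advance and put them in the same table.

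The cost is a few extra models, one table and some wording, with no new data. The change removes the selection but not the multiplicity. The table should say that the intervals are unadjusted and that, with six independent tests, the chance of at least one false positive is about 26.5%.

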6.3 INTERIM ANALYSES

An interim analysis for futility was originally scheduled when approximately 50% of patients had completed 104 weeks of the double-blind treatment period. These results were to be reviewed by the IDMC. If the analysis of the primary endpoint results at the time of this interim analysis indicated that the predictive probability of success for the trial was < 10% for either ADAS-Cog13 or ADCS-ADL, then the committee may recommend that the trial be terminated for futility. No adjustment for multiple comparisons was to be made to the α level for the analysis, as the decision rules for the futility analysis do not allow for the opportunity to stop the study early for overwhelming efficacy. This interim analysis was to be conducted by an independent Data Collection Center and will be reviewed by the IDMC.

There is no interim analysis scheduled for the OLE. However, the Sponsor will review the data on an ongoing basis.

7. DATA COLLECTION AND MANAGEMENT

7.1 DATA QUALITY ASSURANCE

The Sponsor will be responsible for data management of this study, including quality checking of the data. Data entered manually will be collected via EDC using eCRFs. Sites will be responsible for data entry into the EDC system. In the event of discrepant data, the Sponsor will request data clarification from the sites, which the sites will resolve electronically in the EDC system.

The Sponsor will produce an EDC Study Specification document that describes the quality checking to be performed on the data. All electronic data from external vendors will be sent directly to the Sponsor, using the Sponsor's standard procedures to handle and process the electronic transfer of these data.

eCRFs and correction documentation will be maintained in the EDC system's audit trail. System backups for data stored by the Sponsor and records retention for the study data will be consistent with the Sponsor's standard procedures.

All rating scales data will be captured electronically. The symptom-guide facilitated goal-attainment scaling will be entered via a Web-based database. The other scales listed in Section 4.5.6.11 will be recorded directly into device laptop provided by a vendor. All other scales will be completed on paper and entered into the vendor-provided laptop by site staff. This device is designed for entry of data in a manner that is attributable, secure, and accurate in compliance with U.S. FDA regulations for electronic records (21 CFR, Part 11). The device data are available for view access only through secure access to an online Web portal. Only identified and trained users may view the data, and their actions become part of the audit trail. System backups for data stored by the Sponsor and records retention for the study data will be consistent with the Sponsor's standard procedures.

In the event that the device is not working, a paper backup for should be used to collect the rating scales data in Section 4.5.6.11. When the device becomes available, the data should then be entered into the device and recorded that paper backup was used.

7.2 ELECTRONIC CASE REPORT FORMS

eCRFs are to be completed using a Sponsor-designated EDC system. Sites will receive training and have access to a manual for appropriate eCRF completion. eCRFs will be submitted electronically to the Sponsor and should be handled in accordance with instructions from the Sponsor.

All eCRFs should be completed by designated, trained site staff. eCRFs should be reviewed and electronically signed and dated by the investigator or a designee.

At the end of the study, the investigator will receive patient data for his or her site in a readable format on a compact disc that must be kept with the study records. Acknowledgement of receipt of the compact disc is required.

7.3 ELECTRONIC RATING SCALE DATA

Patients, caregivers, and appropriate site staff will use a laptop to record selected rating scales data, including clinician, patient and caregiver-reported data. The data will be transmitted via Web automatically after entry to a centralized database at the vendor. The data may be reviewed by site staff via secure access to an online Web portal.

Once the study is complete, the rating scales data, audit trail, and trial and system documentation will be archived. The investigator will receive patient data for the site in both human- and machine-readable formats on an archival-quality compact disc that must be kept with the study records as source data. Acknowledgement of receipt of the compact disc is required. In addition, the Sponsor will receive all patient data in a machine-readable format on a compact disc.

7.4 SOURCE DATA VERIFICATION

Study monitors will perform ongoing source data verification to confirm that critical protocol data (i.e., source data) entered by authorized site personnel are accurate, complete, and verifiable from source documents.

Source documents (paper or electronic) are those in which patient data are recorded and documented for the first time. They include, but are not limited to, hospital records, clinical and office charts, laboratory notes, memoranda, PROs, evaluation checklists, pharmacy dispensing records, recorded data from automated instruments, copies of transcriptions that are certified after verification as being accurate and complete, microfiche, photographic negatives, microfilm or magnetic media, X-rays, patient files, and records kept at pharmacies, laboratories, and medico-technical departments involved in a clinical trial.

Before study initiation, the types of source documents that are to be generated will be clearly defined in the Trial Monitoring Plan. This includes any protocol data to be entered directly onto the eCRFs and electronically administered rating scales per Section 7.5 (i.e., no prior written or electronic record of the data) and considered source data.

Source documents that are required to verify the validity and completeness of data entered onto the eCRFs must not be obliterated or destroyed and must be retained per the policy for retention of records described in Section 7.6.

To facilitate source data verification, the investigators and institutions must provide the Sponsor direct access to applicable source documents and reports for trial-related

monitoring, Sponsor audits, and IRB/EC review. The investigative site must also allow inspection by applicable health authorities.

7.5 USE OF COMPUTERIZED SYSTEMS

When clinical observations are entered directly into an investigative site's computerized medical record system (i.e., in lieu of original hardcopy records), the electronic record can serve as the source document if the system has been validated in accordance with health authority requirements pertaining to computerized systems used in clinical research. An acceptable computerized data collection system allows preservation of the original entry of data. If original data are modified, the system should maintain a viewable audit trail that shows the original data as well as the reason for the change, the name of the person making the change, and date of the change.

7.6 RETENTION OF RECORDS

Records and documents pertaining to the conduct of this study and the distribution of IMP, including eCRFs, ePRO data (if applicable), Informed Consent Forms, laboratory test results, and study drug inventory records, must be retained by the Principal Investigator for at least 15 years after completion or discontinuation of the study, or for the length of time required by relevant national or local health authorities, whichever is longer. After that period of time, the documents may be destroyed, subject to local regulations.

No records may be disposed of without the written approval of the Sponsor. Written notification should be provided to the Sponsor prior to transferring any records to another party or moving them to another location.

